2.9.1.1 Adverse events of special interest / grouping of AEs

Adverse events related to COVID-19 pandemic are listed.

2.9.2 Deaths

Deaths are listed. A frequency table with absolute numbers, percentages and 95% confidence interval is presented.

2.9.3 Laboratory data

Hematology is listed only. The analysis of other lab parameters are described in section 2.5 and section 2.7.

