8.4.1 Laboratory evaluations

A central laboratory will be used for analysis of all safety specimens collected. Details on the collection, shipment of samples and reporting of results by the central laboratory are provided to investigators in the central laboratory manual.

All abnormal lab results must be evaluated for criteria defining an adverse event and reported as such if the criteria are met. For those lab adverse events, repeated evaluations are mandatory until normalization of the result(s) or until the result is no longer considered clinically significant.

Special clinical laboratory evaluations

Test Category	Test Name
SARS-CoV-2 vaccination antibody response	Serum functional SARS-CoV-2 antibodies
SARS-CoV-2 vaccination T-cell response	Ex vivo IFNy and IL-2 enzyme-linked immunosorbent spot (ELISpot)
Hematology	Blood samples will be collected according to the schedule in Table 8-1, 8-2, 8-3 and Table 8-4. Hematocrit, Hemoglobin, Platelets, Red blood cells, White blood cells, Differential (Basophils, Eosinophils, Lymphocytes, Monocytes, Neutrophils)
B cell count	CD19+/CD20+ B-cell counts. Samples will be collected according to the schedule in Table 8-1, Table 8-2, Table 8-3 and Table 8-4.

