12.5.1 Safety endpoints

For all safety analyses, the safety set will be used. All listings and tables will be presented by cohort.

Safety summaries (tables, figures) include only data from the on-treatment period with the exception of baseline data which will also be summarized where appropriate (e.g. change from baseline summaries). In addition, a separate summary for death including on treatment and post treatment deaths will be provided. In particular, summary tables for adverse events (AEs) will summarize only on-treatment events, with a start date during the on-treatment period (treatment-emergent AEs).

The on-treatment period lasts from the date of first administration of study treatment to 30 days after the last study visit.

Adverse events

All information obtained on adverse events will be displayed by cohort and participant.

The number (and percentage) of participants with treatment emergent adverse events (events started after the first dose of study medication or events present prior to start of double-blind treatment but increased in severity based on preferred term) will be summarized in the following ways:

- by cohort, primary system organ class and preferred term.
- by treatment, primary system organ class, preferred term and maximum severity.
- by treatment, Standardized MedDRA Query (SMQ) and preferred term.

Separate summaries will be provided for study medication related adverse events, death, serious adverse events, other significant adverse events leading to discontinuation, and adverse events leading to dose adjustment.

A participant with multiple adverse events within a primary system organ class is only counted once towards the total of the primary system organ class.

Vital signs

All vital signs data will be listed by treatment group, participant, and visit/time and if ranges are available, abnormalities (and relevant orthostatic changes) will be flagged. Summary statistics will be provided by treatment and visit/time.

Clinical laboratory evaluations

All laboratory data will be listed by treatment group (cohort 1 and 2), participant, and visit/time and if normal ranges are available abnormalities will be flagged. Summary statistics will be provided by treatment and visit/time.

[REDACTED]

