2.7 Analysis of secondary efficacy objective(s)

2.7.1 Secondary endpoints

The secondary endpoints are analyzed descriptively within each cohort. The Efficacy Analysis Set is used for all analyses of the secondary parameters.

The proportion of patients achieving seroconversion³ in SARS-CoV-2 neutralizing antibodies is presented for the time points Month 1, Month 6, and Month 12. Exact confidence intervals (95%, two-sided) are calculated by the Pearson-Clopper method.

The phenotypical parameters are displayed by sample statistics and boxplots per time point (Screening, Month 1, Month 6, and Month 12) by cohort. For the baseline visit the subcohorts are presented. This applies to these parameters:

- CD19+/CD20+ B cells (absolute and relative values)
- CD4+ cells (% of mononuclear cells)
- CD4: IL4 basal and stimulated, IFNg basal and stimulated (%)
- CD4 naïve: IL4 basal and stimulated, IFNg basal and stimulated (%)
- CD4 TCM: IL4 basal and stimulated, IFNg basal and stimulated (%)
- CD4 TEM CD27 – and CD27+: IL4 basal and stimulated, IFNg basal and stimulated (%)
- CD8+ cells (% of mononuclear cells)
- CD8: IL4 basal and stimulated, IFNg basal and stimulated (%)
- CD8 naïve: IL4 basal and stimulated, IFNg basal and stimulated (%)
- CD8 TCM: IL4 basal and stimulated, IFNg basal and stimulated (%)
- CD8 TEM CD27 – and CD27+: IL4 basal and stimulated, IFNg basal and stimulated (%)

³ For derivation of seroconversion see Appendix 5.3.2

All other laboratory data (e. g. number of basal/background spots, spots, quality, comments, mutations and hematology) are listed only.

The MS activity is measured by relapses. The crude annual relapse rate until end of study and the underlying sums (of relapses and patient-years) will be presented.

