2.9.1 Adverse events (AEs)

According to the CSP all adverse events starting in the on-treatment period, i. e. the treatment-emergent AEs, are analyzed.

The on-treatment period lasts from the date of first administration of study treatment⁴ after informed consent to 30 days after the last visit.

⁴ Study treatment is ofatumumab as well as the modRNA vaccine.

The number (and percentage) of subjects with treatment-emergent adverse events will be summarized in the following ways:

- by treatment group (cohort 1 and 2), primary system organ class and preferred term.
- by treatment group (cohort 1 and 2), primary system organ class, preferred term and maximum severity
- by type of modRNA (Biontech/Pfizer versus Moderna), primary system organ class and preferred term.

A subject with multiple AEs within a MedDRA primary system organ class is only counted once towards the total of the primary system organ class.

A subject with multiple AEs within a preferred term is only counted once towards the total of the preferred term class.

Separate summaries will be provided for study medication related AEs, death, SAEs, AEs leading to discontinuation and adverse events leading to dose adjustment.

The absolute and relative frequency of COVID-19 infections is presented.

Deaths and serious adverse events are listed in addition. Deaths outside the on-treatment period are listed in addition.

Rates of COVID-19 infections and the rate of COVID-19 infections starting ≥ 7 days after the 2nd vaccination are displayed. All COVID-19 infections are listed with the dates of all COVID-19 vaccinations.

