2.15 Interim analysis

See section 1.1 Study design.

3 Sample size calculation

The sample size of 20 participants per arm is selected based on need for early availability of results for the current covid-19 pandemic and the feasibility to recruit sufficient participants. This sample size of 20 subjects will provide estimates of proportion responded with margin of error (half-width of a 95% confidence interval) of 20.1%, 19%, and 17.5% corresponding to response rates of 70%, 75%, and 80%, respectively. Adjusting for 10% drop-out, 22 subjects will be enrolled in each arm. In case of fast recruitment the sponsor is allowed to increase sample size in each arm by up to 10 additional patients to support the generation of meaningful data in a larger sample size.

4 Change to protocol specified analyses

The efficacy analysis set was defined in such a way that it can be applied to all efficacy analyses. With regard to the primary parameter, there is no change in content compared to the definition in the study protocol.

5 Appendix

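### The SAP reduces hematology to a listing and has no SMQ adverse event table, and its section 4 records neither departure from Protocol 12.5.1

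*SAP*

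**What the plan says.** **Protocol.** Section 8.4.1 names hematology as a laboratory test category: hematocrit, hemoglobin, platelets, red and white cell counts and a five-part differential. Footnote 3 of Tables 8-1 to 8-4 makes a hematology set part of the scheduled blood sample. Section 12.5.1 requires all laboratory data to be listed by group, participant and visit, and continues: "if normal ranges are available abnormalities will be flagged. Summary statistics will be provided by treatment and visit/time". The same section sets out three summaries of treatment-emergent adverse events, the third of them "by treatment, Standardized MedDRA Query (SMQ) and preferred term".

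**SAP.** Section 2.9.3 states "Hematology is listed only" and refers to sections 2.5 and 2.7 for other laboratory parameters. Section 2.7.1 says the same in a parenthesis that ends "mutations and hematology) are listed only". Section 2.9.1 also has three adverse event summaries. The first two correspond to the protocol's, but the third is "by type of modRNA (Biontech/Pfizer versus Moderna), primary system organ class and preferred term". SMQs appear nowhere in the SAP text, including 2.9.1.1, the section on grouping of adverse events.

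SAP section 4 is the place for changes to protocol-specified analyses. It reads "The efficacy analysis set was defined in such a way that it can be applied to all efficacy analyses", adds that the primary parameter is unchanged in content, and says nothing about safety.

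**The concern.** Safety and tolerability is a stated secondary objective in both documents. The patients receive a cell-depleting antibody close to vaccination, and a blood count with differential is taken at the scheduled sampling visits. In cohort 1 the Baseline and Month 1 samples normally precede ofatumumab and the later ones follow its start, so a by-visit summary would show counts before and on treatment in the same patients.

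Under the SAP as written, those counts reach a table only when an investigator reports an abnormal value as an adverse event. Protocol 10.1.1 limits that to values that cause signs or symptoms, are judged clinically significant or require therapy. A moderate shift across a cohort, with no single value striking enough to report, would appear in no planned table.

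There is also a question of transparency. A reader of SAP section 4 would conclude that the safety outputs follow the protocol, and on these two points they do not.

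**Working it through.** The documents state no figure to reproduce, and the point rests on no sample size or power calculation. The check sets each commitment in Protocol 12.5.1 against the SAP.

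| Protocol 12.5.1 output | SAP text | Result | In SAP section 4? |
|---|---|---|---|
| Laboratory listing | 2.7.1, 2.9.3: hematology listed | Met | n/a |
| Abnormal values flagged where ranges exist | Not mentioned | Silent | No |
| Laboratory summary statistics by treatment and visit | 2.7.1, 2.9.3: hematology listing and nothing more | Contradicted for hematology | No |
| Adverse events by system organ class and preferred term | 2.9.1, first summary | Met | n/a |
| Same, with maximum severity | 2.9.1, second summary | Met | n/a |
| Adverse events by SMQ and preferred term | 2.9.1, third summary is by vaccine type | Absent | No |

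**Which laboratory parameters are affected.** Protocol 8.4.1 gives hematocrit, hemoglobin, platelets, red cells and white cells (5) plus basophils, eosinophils, lymphocytes, monocytes and neutrophils (5), so 5 + 5 = 10 hematology parameters. The SAP text summarises none of them.

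The other laboratory categories in 8.4.1 are covered:
- CD19+/CD20+ B cells (absolute and relative) and CD4+ and CD8+ subsets have sample statistics and boxplots at Screening and Months 1, 6 and 12 (SAP 2.7.1).
- ELISpot results are tabulated by visit (SAP 2.5.4).
- Neutralizing antibodies are presented as seroconversion rates (SAP 2.7.1).

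The laboratory gap is therefore hematology alone.

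**Which visits could be summarised.** SAP 2.1.3 gives six time points for subcohorts 1a and 2a (Baseline, Week 1, Months 1, 6, 12 and 18) and four for 1b and 2b (Baseline, Months 1, 6 and 12). A cohort-level table can use the four common time points. Week 1 and Month 18 describe only the *a* subcohorts.

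**Whether the hematology restriction could be an oversight.** It is stated in two separate sections. By contrast, SAP 2.9.4.2 plans changes from screening to each time point for pulse, blood pressure and body weight. By-visit safety summaries are thus within the planned programming, and hematology was set apart from them.

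**The case against.** The strongest reply is that little is lost. The SAP summarises the cells that ofatumumab targets, together with the CD4+ and CD8+ subsets. Every hematology value stays in the listing, and Protocol 8.4.1 has each abnormal result assessed against the adverse event criteria. Planned size is about 20 patients per cohort, so a listing can be read. The study is descriptive throughout.

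On SMQs, the protocol names none. The same paragraph refers to double-blind treatment in an open-label study, which suggests carried-over template text. The table and listing shells cited in SAP 2.2.1 are not among the documents, and the SAP section between 2.7 and 2.9 is blacked out. An SMQ table or a flagged listing could exist there.

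Much of this stands, and it rules out several stronger readings that a reader might infer:
- *That the SMQ table is the only grouping of related terms.* SAP 2.9.1 tabulates events by system organ class and preferred term, gives frequencies of COVID-19 infections, and gives the rate of those starting at least 7 days after the second vaccination. Infections are already grouped.
- *That any lymphocyte change would go unseen.* B-cell and CD4+/CD8+ summaries are planned. What is missing is the total lymphocyte count.
- *That the SAP rejects flagging.* It is silent. The protocol itself makes flagging conditional on normal ranges being available.
- *That the protocol requires shift tables or change from baseline for hematology.* It asks for summary statistics by visit. Change from baseline appears in 12.5.1 only as an example of when baseline data are summarised.

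The reply does not remove the explicit restriction in SAP 2.9.3 and 2.7.1. Table shells cannot supply a summary that the SAP text rules out, and they do not make good an incomplete section 4. The undefined SMQ line is a good reason to remove that table, but the reason is not recorded.

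**Conclusion.** The documents conflict on hematology, and the SMQ table has been replaced by a table by vaccine type. Neither departure is declared. As a result, cohort-level changes in ten parameters (neutrophils, total lymphocytes, platelets, red-cell measures, total white cells and the rest of the differential) appear in no table that the SAP text plans.

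The consequence is confined to descriptive safety reporting. The primary endpoint, its confidence interval and the secondary immune-response outputs are unaffected. It would go too far to say that nothing can be learned from the hematology data, because every value is listed and clinically relevant abnormalities enter the adverse event tables.

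The finding on hematology rests on explicit wording in both documents. The finding on SMQs rests on their absence from the SAP text and would be weaker if the shells contain such a table. The correction should be made because it is cheap and serves a stated objective.

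**What to change.** 1. **SAP 2.9.3.** Replace the sentence restricting hematology to a listing with: *Hematology parameters are summarised on the SAF by descriptive statistics by cohort and visit at Baseline and Months 1, 6 and 12, and at Week 1 and Month 18 for subcohorts 1a and 2a only. Values outside the central laboratory ranges are flagged in the listing.*
2. **SAP 2.7.1.** Remove hematology from the sentence on laboratory data that are not summarised, so that the two sections agree.
3. **SAP 2.9.1 or section 4.** Either restore the adverse event table by SMQ and preferred term, naming the SMQs to be used, or record its removal with a reason in section 4. The added table by vaccine type should be noted there too.
4. **If the sponsor prefers to keep hematology as a listing,** section 4 should say so and give the reason.

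The cost is one set of by-visit tables for ten parameters, a flag in an existing listing, and either one adverse event table or a sentence in section 4. No additional samples or visits are needed.

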2.9.4 Other safety data

2.9.4.1 Physical examination

Clinically significant findings which were not present at screening but at any later visits are displayed by a frequency table.

2.9.4.2 Vital signs

The changes from screening to Week 1, to Month 1, to Months 6, to month 12, and to Month 18 as well as differences between last and first value are displayed for pulse, systolic/diastolic blood pressure and body weight.

2.10 Pharmacokinetic endpoints

Not applicable.

2.11 PD and PK/PD analyses

Not applicable.

2.12 Patient-reported outcomes

Not applicable.

2.13 Biomarkers

Not applicable.

2.14 Other Exploratory analyses

Not applicable.

2.15 Interim analysis

See section 1.1 Study design.

3 Sample size calculation

The sample size of 20 participants per arm is selected based on need for early availability of results for the current covid-19 pandemic and the feasibility to recruit sufficient participants. This sample size of 20 subjects will provide estimates of proportion responded with margin of error (half-width of a 95% confidence interval) of 20.1%, 19%, and 17.5% corresponding to response rates of 70%, 75%, and 80%, respectively. Adjusting for 10% drop-out, 22 subjects will be enrolled in each arm. In case of fast recruitment the sponsor is allowed to increase sample size in each arm by up to 10 additional patients to support the generation of meaningful data in a larger sample size.

4 Change to protocol specified analyses

The efficacy analysis set was defined in such a way that it can be applied to all efficacy analyses. With regard to the primary parameter, there is no change in content compared to the definition in the study protocol.

5 Appendix

5.1 Imputation rules

No imputations will be done except:

- a. If differences between dates are calculated, partial dates are replaced by 15/6 for days/month. If negative date differences result from this replacement, the value is set to 0.

b. According to the Note to File dated 29 September 2023 the quantitative values and spots of IFGg and IL-2 were corrected (i. e. set to a missing value) when the respective qualitative assessment was “not evaluable”. This applied both to parameters “PAN corona” and “SARS CoV-2. This correction was performed also when the value for qualitative assessments was “missing” (see Note to file dated 20 Oct 2023).

5.2 Treatment-emergent adverse events

Treatment emergent AEs are those which start in the on-treatment period. The on-treatment period lasts from the date of first administration of study medication after informed consent to 30 days after the last visit.

The date of first administration of study medication is the date of 1st vaccination or the date of first ofatumumab at or after screening whichever is earlier.

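### The protocol defines treatment-emergent adverse events in two conflicting ways, and the SAP adopts the narrower one without recording the choice, so events that begin before the first study dose and worsen after it are left out of the tables

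*SAP*

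**What the plan says.** Protocol 12.5.1 states the scope of the adverse event tables twice. The general safety paragraph says that these tables "will summarize only on-treatment events, with a start date during the on-treatment period (treatment-emergent AEs". Under the Adverse events subheading, the paragraph that specifies the tables by system organ class and preferred term counts events that start after the first dose, and also "events present prior to start of double-blind treatment but increased in severity based on preferred term".

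SAP 2.9.1 takes up the first form and attributes it to the protocol: "According to the CSP all adverse events starting in the on-treatment period, i. e. the treatment-emergent AEs, are analyzed". SAP 5.2 repeats it: "Treatment emergent AEs are those which start in the on-treatment period". SAP 5.2 also fixes when the period opens: it takes the earlier of two dates, that of the first vaccination and that of the first ofatumumab dose given from screening onwards.

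SAP 4, which lists changes to the protocol-specified analyses, mentions only the efficacy analysis set.

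**The concern.** Safety and tolerability is a stated secondary objective (Protocol Table 2-1, SAP 1.2), and these tables are its main summary. Whether a worsened pre-dose event belongs in them decides which events are counted. The protocol answers both ways, and the SAP follows one answer without noting that the other exists.

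A reader of the study report who has the protocol's table paragraph in mind would assume that worsened events are included when they are not. Relative to that broader definition, the omission can only lower the counts.

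The broader wording also cannot be programmed as it stands. Its reference date is the start of a double-blind treatment, whereas the study is open-label and Protocol 6.4 marks blinding as not applicable.

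**Working it through.** The plan states no figure on this point, so the check is a comparison of the texts followed by a classification of events.

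**Step 1. The rules side by side**

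| Source | Starts on treatment | Present before, worsens on treatment |
|---|---|---|
| Protocol 12.5.1, general safety paragraph | counted | not counted |
| Protocol 12.5.1, Adverse events paragraph | counted | counted |
| SAP 2.9.1 | counted | not counted |
| SAP 5.2 | counted | not counted |
| SAP 4 | no entry | no entry |

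**Step 2. Which events the choice affects**

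Protocol 10.1.1 collects adverse events from consent and puts conditions already present at consent into medical history. Four cases follow.

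- Starts on or after the first study dose: counted under both rules.
- Starts between consent and first dose and does not worsen: counted under neither.
- Starts between consent and first dose, worsens after the dose and stays one record with its pre-dose start date: counted only under the broader rule.
- Present at consent and worsens on treatment: if the worsening is entered as an adverse event with its own start date, it counts under both. Protocol 8.4 points that way for significant examination findings made after consent.

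The rules therefore differ mainly in the third case.

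**Step 3. Who has a pre-dose window**

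The start of the period is read here as the first vaccination or ofatumumab dose after consent, as SAP 2.9.1 says.

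- Cohort 1: Protocol 4.5 allows 1 to 12 weeks between screening and the vaccination appointment. Protocol 3 places baseline about one week before vaccination and lets cohort 1a combine screening and baseline.
- Cohort 2 patients who start ofatumumab in the study may do so at screening, which leaves almost no window.
- Cohort 2 patients already on ofatumumab may have screening and baseline together about one week before vaccination (footnotes to Protocol Tables 8-3 and 8-4), so their window is short.

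**Step 4. Scale per patient**

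The tables count patients, once per system organ class and once per preferred term. One extra patient moves a row by 1/n:

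- n = 20 (planned per arm): 1/20 = 5.0 percentage points
- n = 22 (with the drop-out allowance): 1/22 = 4.5 points
- n = 30 (20 plus the optional 10): 1/30 = 3.3 points

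A row moves only if that patient is not already counted in it. The number of patients in the third case is not given, so no total can be computed.

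**Step 5. Whether the broader rule can be applied**

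Protocol 10.1.1 records a CTCAE grade for each event and requires changes in severity to be assessed at every visit. The information is collected. The documents do not say whether the eCRF stores a date for each grade change.

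**The case against.** The strongest reply is that the SAP did follow the protocol. The general safety paragraph of Protocol 12.5.1 ties the label treatment-emergent to a start date in the on-treatment period, and the SAP reproduces it. On that view the citation of the protocol is accurate and SAP 4 had nothing to record. The contrary wording is a parenthesis naming a treatment phase that does not exist here, which suggests carried-over text. This stands to the extent that the root fault is a contradiction in the protocol. A reader might infer that the SAP plainly departed from the protocol; the documents do not support that. What remains is that the protocol has two rules for the same tables and no document says which governs.

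The affected group is also narrow (Step 2), the analyses are descriptive, and Protocol 12.5.1 promises a display of all adverse event information by participant, so the events need not be lost from view. These points limit the size. They do not settle which events the tables contain.

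A reader might also infer a shown bias between cohorts from the 1 to 12 weeks in cohort 1. The documents support only a possible difference: the actual window can be about a week, and no between-cohort test of adverse events is planned.

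**Conclusion.** The point holds as an unresolved conflict of definitions that the SAP settled silently in favour of the narrower count. It affects events that begin between consent and first study dose, worsen on treatment and keep their pre-dose start date. Relative to the broader protocol definition the effect is towards fewer events. Its total size cannot be derived and is probably small. This assumes that worsening is kept within the existing record; where sites open a new record at worsening, the two rules agree.

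A reader might infer a second undercount from SAP 5.1: "If differences between dates are calculated, partial dates are replaced by 15/6 for days/month". If a reaction's start day is missing and set to the 15th, a first dose later in that month would seem to follow the reaction. The documents do not support this. The rule applies only when date differences are calculated, and the sentence after it sets any negative difference that results to 0. Take a reaction on the day of dosing:

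- Day missing, 30-day month: the 15th precedes the dose for 30 − 15 = 15 of 30 dose days without the floor at 0, and for 0 of 30 with it.
- Only the year known: 15 June is day 166, so 365 − 166 = 199 of 365 dose days without the floor, and 0 of 365 with it.

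Nor is there a single direction of error. Over all pairs of event day and dose day in a 30-day month, 30 × 29 / 2 = 435 events are truly pre-dose and 30 × 31 / 2 = 465 fall on or after the dose. With the floor, all 435 pre-dose events would count as treatment-emergent. Without it, 120 of 465 would be missed and 105 of 435 wrongly included. What is left is missing detail: SAP 5.1 opens with "No imputations will be done except", and SAP 5.2 does not say how an event with a partial start date is classified.

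**What to change.** - **SAP 5.2, with SAP 2.9.1 brought into line:** define an adverse event as treatment-emergent if it starts, or increases in CTCAE grade, on or after the first study treatment following consent and within the on-treatment period. Say how worsening is identified, for example by comparing the highest grade before and after first treatment within a preferred term.
- **Protocol 12.5.1:** reconcile the two paragraphs so that both give this definition, and replace the reference to double-blind treatment with study treatment.
- **If the sponsor prefers start date alone:** remove the worsening clause from the protocol, or record and justify the choice in SAP 4.
- **Optional clarification:** add one sentence in SAP 5.2 on how an event with a partial start date is classified.

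The cost is a few sentences, a small derivation change and a slightly higher event count. If the eCRF holds no date for grade changes, the worsening rule will also need a check of the visit-level severity assessments.
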